#### 2.9.9 Early withdrawal and lost to follow-up

Study subjects are free to withdraw from the investigation at any time without having to justify their reasons and without affecting their relationship with the investigator. An investigator may also withdraw a subject from the study at any time if it is determined to be in the subject's best interests.

A subject's future management will not be changed by a decision, voluntary or otherwise, to withdraw from the study. All reasonable efforts should be made to retain subjects until completion of the clinical study. Reasons for termination or withdrawal include but are not limited to the following:

- Subject death
- Subject request
- Subject lost to follow-up. A subject is considered "lost to follow-up" after a minimum of 2 documented attempts to reach the subject by phone call by a member of the study staff and an unanswered certified letter sent to the subject's last known address by a traceable method (eg, certified mail, courier, commercial shipping/transport company)
- Subject's participation terminated by the investigator

- Study terminated by the sponsor

For any subjects with early withdrawal or termination, termination information will be recorded in the subject's records and the date of last contact with the subject noted on the End of Study CRF.

#### 2.9.10 End of study

Subjects randomized to the control arm who do not crossover to balloon dilation treatment are exited upon completion of the 6-week crossover evaluation.

Participation in the study is considered complete for all balloon dilation and crossover subjects upon completion of the 12-month postprocedure visit.

If a subject has an XprESS device inserted transnasally but does not undergo a balloon dilation procedure, the subject will be followed to the 6-week postprocedure visit and then discontinued from the study unless the subject has an ongoing adverse event (AE). If the subject has an ongoing AE at the 6-week postprocedure visit, the subject will be followed until AE resolution or 12 months post procedure, whichever comes first.

An End of Study CRF will be completed when the subject has completed their last required follow-up visit or at the time of withdrawal or lost to follow-up if the subject discontinues the study prematurely.

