## 2.3 Study endpoints

### 2.3.1 Primary endpoints

The following measures will be collected as the primary endpoints:

- Comparison of mean change in overall ETDQ-7 score from baseline to 6 weeks between balloon dilation arm and control arm
- Complication rate

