## 2.7 Data analyses

Summary statistics will be calculated for all study endpoints. Categorical variables will be summarized using frequency distributions and continuous variables will be summarized with means, standard deviations, and ranges. Confidence intervals (95% CI) may be computed for select study endpoint measures. The primary efficacy endpoint will be tested at a 1-sided alpha level of 0.025. The secondary endpoint of the mean change in the overall ETDQ-7 score from baseline to follow-up in subjects treated with balloon dilation will be tested at a 2-sided alpha level of 0.05.

Subjects who are randomized but drop out before receiving their randomized treatment (balloon dilation or completion of the 6-week continued medical therapy) will not be included in the data analysis.

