#### *Complication rate*

A complication is defined as a serious adverse event that is device-related or procedure-related as noted in **Section 6**. The parameter of interest is the percent of subjects who experience 1 or more complications from the time of the index procedure through the 6-month follow-up.

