### 3.2 Potential risks

Study subjects will be informed of all known potential side effects and complications associated with study treatment and study assessments before consenting for the study. The risks associated with participating in the study are the same as those that the subject would have if treated with transnasal Eustachian tube balloon dilation outside of the study. These potential risks include:

- Complications from anesthesia
- Pain
- Bruising and swelling
- Bleeding
- Infection
- Continued or worsening symptoms
- Revision surgery
- Tinnitus
- Preauricular emphysema
- Damage to the ET
- Patulous ET
- Permanent hearing loss
- Tympanic membrane damage
- Carotid artery damage
- Cerebrospinal fluid leak

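### The primary complication rate runs to 6 months, but a subject with the device inserted and no dilation performed leaves at 6 weeks unless an adverse event is ongoing, and the rate's denominator is not defined

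*Combined protocol and SAP*

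**What the plan says.** Section 2.3.1 of the combined protocol and SAP lists "Complication rate" as a primary endpoint beside the ETDQ-7 comparison. Section 2.10.1 gives the definition: "A complication is defined as a serious adverse event that is device-related or procedure-related". The parameter is the "percent of subjects who experience 1 or more complications from the time of the index procedure through the 6-month follow-up". Neither sentence requires that a balloon was inflated, and neither states which subjects form the denominator.

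Section 2.9.10 has a separate rule for one group: "If a subject has an XprESS device inserted transnasally but does not undergo a balloon dilation procedure", then "the subject will be followed to the 6-week postprocedure visit and then discontinued from the study unless the subject has an ongoing adverse event (AE". Where an adverse event is ongoing at that visit, "the subject will be followed until AE resolution or 12 months post procedure, whichever comes first".

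The only rule on who is analyzed is in Section 2.7. It leaves out of the data analysis "Subjects who are randomized but drop out before receiving their randomized treatment (balloon dilation or completion of the 6-week continued medical therapy". It does not distinguish efficacy from safety, and no safety set is defined elsewhere.

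**The concern.** A subject with the device inserted has had anesthesia and instrumentation. Section 3.2 lists risks that do not depend on inflating a balloon, beginning with "Complications from anesthesia". Section 2.9.10 shows that the sponsor expected some procedures to end this way. These subjects can therefore have an event that meets the complication definition, yet their planned observation is much shorter than the endpoint window and their place in the denominator is unstated.

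Two separate things are at stake.

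- **Ascertainment.** A related SAE that starts after the 6-week exit would not be collected by any scheduled contact. Section 6.1 also ties adverse events to the follow-up period, so after exit there is no clear basis for recording one.
- **Inclusion.** If the Section 2.7 exclusion is applied to safety, a subject and any complication that subject had could be left out. If that choice is made once events are known, a primary safety result in a 510(k) file is open to challenge.

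**Working it through.** **Plan's own figure.** The complication rate has no stated sample size, expected rate or performance goal, so there is nothing to reproduce for it. The only stated sample size is for the ETDQ-7 comparison (Section 2.6: difference 1.3, SD 1.3, 1-sided alpha 0.025). A noncentral-t calculation gives 80.7% power at 17 per arm and 78.1% at 16, so 17 per arm is confirmed. This point does not affect it.

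**Step 1: observed share of the window.** Inputs are the exit at 6 weeks (Section 2.9.10), the visit window of ±7 days (Table 1) and an endpoint window of 6 months, taken as 26 weeks.

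- Unobserved share = (26 − 6)/26 = 76.9%.
- Exit at 7 weeks: (26 − 7)/26 = 73.1%. Exit at 5 weeks: (26 − 5)/26 = 80.8%.

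This is a share of calendar time, not of expected events. The documents give no late-onset rate.

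**Step 2: which events are missed.**

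| Onset and status | Collected? |
|---|---|
| Starts and resolves by the 6-week visit | Yes: adverse events are recorded at the procedure and at 6 weeks (Table 1) |
| Starts by 6 weeks and is ongoing at the visit | Yes: followed to resolution or 12 months (Section 2.9.10) |
| Starts between exit and 6 months | No scheduled collection |

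The exception for an ongoing event lasts only until that event resolves, so such a subject may also leave before 6 months. Section 2.7.2 plans missing-data analyses for the primary efficacy endpoint only. If an exited subject is counted, the plan does not say how the unobserved weeks are handled.

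**Step 3: whom the Section 2.7 exclusion could reach.** It concerns randomized subjects who have not received their randomized treatment.

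- Phase 1 (10 subjects): not randomized, so not reached.
- Crossover subjects: their randomized treatment was the 6 weeks of medical therapy, which they completed, so not reached.
- Randomized to dilation: 40 × 1/2 = 20 subjects, reached on one reading.

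The 6-week exit in Section 2.9.10 has no such limit and applies to all three groups.

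**Step 4: effect of one subject.** The documents do not give the frequency of insertion without dilation, so the denominators are assumptions. I use 25, the 510(k) minimum in Section 2.4 taken as a round total, and 50, which is 10 + 20 + 20 if every control subject crosses over. Limits are the upper ends of two-sided exact (Clopper-Pearson) 95% intervals: the 0.975 quantile of Beta(x + 1, n − x), which for x = 0 is 1 − 0.025^(1/n).

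| Total with procedure started | Subject left out | Included, no complication | Included, with complication |
|---|---|---|---|
| 25 | 0/24 = 0%, upper 14.2% | 0/25 = 0%, upper 13.7% | 1/25 = 4.0%, upper 20.4% |
| 50 | 0/49 = 0%, upper 7.3% | 0/50 = 0%, upper 7.1% | 1/50 = 2.0%, upper 10.6% |

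If the subject has no complication, inclusion slightly lowers the upper limit. The result moves unfavorably only if there was a complication. The last column describes inclusion in the analysis; it is not a consequence of the 6-week exit alone.

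**The case against.** The strongest reply is that the events most to be feared from a difficult insertion appear early, and the protocol collects those. Adverse events are recorded at the procedure and at 6 weeks, and an ongoing one is followed to resolution or 12 months. That stands. It confines the follow-up gap to new-onset related SAEs after exit.

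The second reply is that exclusion is not stated. A subject who has an index procedure, attends the 6-week visit and is then discontinued by protocol is not naturally a drop-out, and the complication definition counts subjects from the index procedure without requiring dilation. That also stands, as the more natural reading. But the documents state neither inclusion nor exclusion, and Section 2.7 is the only population rule.

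A reader might infer more than the text supports:

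- **That a subject given anesthesia but with no device inserted has no safety follow-up.** Section 2.9.7 schedules subjects randomized to dilation and crossover subjects for visits to 12 months, with adverse events at each. The early exit is triggered only by insertion without dilation.
- **That the rate would describe successful dilations only.** The exit applies when no dilation is performed at all. A subject with one failed tube and the other dilated stays in follow-up.
- **That a mismatch with technical success is itself an error.** That endpoint is counted per tube and complications per subject, so the denominators differ by design.

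**Conclusion.** The point holds in a limited form. Section 2.9.10 and the complication definition in Section 2.10.1 do not match for related SAEs that begin after a 6-week exit, which leaves about 77% of the window (73% to 81% with the visit window) without scheduled collection for these subjects. Separately, the safety denominator is undefined, and Section 2.7 can on one reading remove such a subject if randomized to dilation.

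Few subjects are likely to be affected, but the study is small: one such subject with a complication is worth 2.0 percentage points at a total of 50 and 4.0 at a total of 25. This rests on assumed denominators and on a single event. The documents give neither the frequency of insertion without dilation nor the rate of late-onset SAEs, so the size of any bias cannot be estimated. Incomplete collection can only lower the observed count. Exclusion lowers the rate only if the excluded subjects have complications more often than the rest.

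**What to change.** Three wording changes:

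1. **Section 2.10.1, complication rate.** Define the denominator as all subjects in whom the dilation procedure was started, whether or not a balloon was inflated, covering Phase 1, randomized-to-dilation and crossover subjects.
2. **Section 2.7.** State that the exclusion of randomized subjects who leave before treatment does not apply to safety analyses.
3. **Section 2.9.10.** Reconcile it with Section 2.10.1 by continuing AE and SAE collection for subjects with insertion but no dilation through the 6-month endpoint window. Telephone contact is enough.

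The cost is a few sentences and a few extra contacts. The sample size and study treatment do not change. The reported complication rate may become slightly less favorable.

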### 2.10 Study assessments and data collection

Study data will be collected according to Good Clinical Practices using paper CRFs completed at the investigational center. CRFs will be collected from the centers and will be entered into a ClinDex database by Entellus staff using 2-pass entry procedures. The data will be reviewed by Entellus staff and any queries will be documented and submitted to the investigational center for clarification.

The required study assessments for each specified interval are outlined in the **Section 2.9**. See **Table 1** for an overview of the required study assessments at each follow-up visit. Each subject's follow-up schedule is based on the date of randomization (control arm) or the study procedure (balloon dilation and crossover arms).

#### 2.10.1 Primary and secondary endpoint assessments

##### *Mean change in overall ETDQ-7 score*

The Eustachian Tube Dysfunction Questionnaire (ETDQ-7) is a standardized, 7-item questionnaire designed to assess quality of life associated with Eustachian tube dysfunction. The 7 dimensions of the questionnaire are pressure, pain, feeling clogged, cold/sinusitis problems, crackling/popping, ringing, and feeling muffled. Each item is assessed on a 1 (no problem) to 7 (severe problem) scale and an overall score, which is the mean of the 7 dimension scores, is calculated. The questionnaire is designed to be self-completed by the subject. ETDQ-7 questionnaires will be completed at baseline and at all study visits. Changes in overall ETDQ-7 scores will be based on the mean change between the baseline assessment (or 6-week crossover

evaluation for crossover subjects) and each follow-up assessment. Standard treatment effect size may also be calculated for the mean overall ETDQ-7 score. The ETDQ-7 CRF may be considered a source document if completed directly by the subject on the CRF.

#### *Complication rate*

A complication is defined as a serious adverse event that is device-related or procedure-related as noted in **Section 6**. The parameter of interest is the percent of subjects who experience 1 or more complications from the time of the index procedure through the 6-month follow-up.

#### *Technical success*

Technical success will be collected for each Eustachian tube in which dilation is attempted. Success of the XprESS device will be calculated as the number of successful dilations divided by the number of ETs with dilation attempts. Success is defined as an attempt where the XprESS device is successfully delivered to the target location, inflated, deflated, and withdrawn from the treated Eustachian tube.

#### *Revision dilation rate*

Revision dilation is defined as any repeat balloon dilation procedure performed on an ET that was initially treated with an XprESS device. The parameter of interest is the percent of subjects who experience 1 or more revision dilations during the study.

### 2.10.2 Other measure assessments

#### *General quality of life assessment*

Quality of life regarding general health will be assessed using the EuroQol (EQ-5D).

The EQ-5D is a standardized questionnaire used to evaluate general health-related quality of life. The questionnaire is made up of 5 questions (1 for each health dimension measured: mobility, self-care, usual activities, pain/discomfort, and anxiety/depression) and a visual analog scale (VAS) to indicate overall health on a scale of 0 to 100. Each health dimension has 5 possible responses: no problems, slight problems, moderate problems, severe problems, or extreme problems. The questionnaire is designed to be self-completed by the subject. The EQ-5D questionnaire will be completed at all study visits. The EQ-5D CRF may be considered a source document if completed directly by the subject on the CRF.

#### *Procedure pain*

The procedure pain assessment will be collected before discharge from each subject who undergoes the dilation procedure with local anesthesia alone. Pain will be assessed using an 11-point VAS. The Procedure CRF may be considered the source document for the procedure pain assessment.

#### *Otoscopy findings*

Otoscopy examinations will be performed at baseline and at each follow-up visit. The examination will include assessment of the tympanic membrane (ear drum) for color, translucency, mobility, shape (bulging, retraction), and the appearance of bubbles. The ear canal

will be observed for edema, fluid/pus, or cerumen (wax). For evaluation, otoscopy findings will be categorized as normal (within normal limits) or abnormal (1 or more characteristic not within normal limits). Results of the otoscopic examination will be documented on the Baseline or Follow-up CRF, as appropriate.

#### *Tympanometry*

Tympanometry will be performed at baseline and at each follow-up visit. The test will be performed with a 226 Hz signal and a copy the tympanogram will be filed with the subject study files. The following parameters from the tympanogram will be documented on the Baseline or Follow-up CRF, as appropriate:

- Peak pressure (daPa)
- Compliance (cm^3)
- Ear canal volume (mL)
- Type (A, B, or C)

#### *Valsalva maneuver*

Each subject will attempt to perform a Valsalva maneuver at baseline and at each follow-up visit after tympanometry is completed. The maneuver is performed by forcing expiration with closed mouth and nostrils which increases the pressure in the middle ear. This typically results in opening of the Eustachian tube with relief of ear congestion. Popping and/or clicking are often heard during the maneuver. If the subject does not experience clearing, popping, or clicking in the ears after attempting the maneuver, the result is considered negative. Results of the Valsalva maneuver will be documented as appropriate.

#### *Ear infection frequency and healthcare visits*

The number of ear infections experienced in the 12-month period before enrollment will be recorded at the baseline visit. At each follow-up visit, the number of ear infections since the last visit will be recorded.

Similarly, the number of physician/nurse visits for ETD-related issues will be recorded and compared between the 12 months before and 12 months after balloon dilation.

#### *Subject satisfaction*

At each follow-up visit, balloon dilation and crossover subjects will be asked to indicate their satisfaction with the procedure outcome and whether they would recommend the procedure to their friends/family. The subject satisfaction questions will be documented on the ETDQ-7 CRF, which may be considered the source document for the satisfaction ratings.

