## 2.9 Methods and procedures

Study methods and procedures are described below. An overview of the required Phase 2 study assessments at each follow-up visit is provided in **Table 1**. Each subject's follow-up schedule is based on the date of randomization (control arm) or the study procedure (balloon dilation arm and crossover subjects).

Table 1. Phase 2 Study Assessment Schedule

Study evaluation	Baseline Within 60 days of procedure for balloon dilation arm	6-Week crossover evaluation (control arm only) ± 7 days	Procedure Within 60 days of baseline or 6-week crossover evaluation	6-Week post procedure ± 7 days	3-Month post procedure ± 15 days	6-Month post procedure ± 30 days (for 510(k) and publication)	12-Month post procedure ± 45 days (for publication)
Informed consent	✓						
Eligibility assessment	✓	✓					
Demographics/history	✓						
CT scan without contrast	✓ a						
Symptoms/exam	✓	✓		✓	✓	✓	✓
Medications b	✓	✓	✓	✓	✓	✓	✓
Nasal endoscopy	✓	✓		✓	✓	✓	✓
Otoscopy examination	✓	✓		✓	✓	✓	✓
Tympanometry	✓	✓		✓	✓	✓	✓
Valsalva evaluation	✓	✓		✓	✓	✓	✓
EQ-5D questionnaire	✓	✓		✓	✓	✓	✓
ETDQ-7 questionnaire	✓	✓		✓	✓	✓	✓
Ear infection assessment	✓ c			✓	✓	✓	✓

Study evaluation	Baseline Within 60 days of procedure for balloon dilation arm	6-Week crossover evaluation (control arm only) ± 7 days	Procedure Within 60 days of baseline or 6-week crossover evaluation	6-Week post procedure ± 7 days	3-Month post procedure ± 15 days	6-Month post procedure ± 30 days (for 510(k) and publication)	12-Month post procedure ± 45 days (for publication)
Audiologic examination	✓					✓	
Pregnancy test (when applicable)	✓		✓				
Procedure pain			✓ d				
Technical success			✓				
Device malfunction			✓				
Adverse events		✓	✓	✓	✓	✓	✓
Revision dilation or additional surgery				✓	✓	✓	✓
Subject satisfaction				✓	✓	✓	✓

a The eligibility CT scan can be performed within 6 months of enrollment.  
b Only ENT-related medications will be recorded (eg, antibiotics, steroids, allergy treatment, decongestants).  
c At baseline, determine the number of ear infections in the 12-month period before enrollment.  
d The pain scale should be completed before discharge from the index procedure. Subjects treated under general anesthesia are not required to assess procedure pain.

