#### 2.9.7 Follow-up visits

Subjects randomized to the control arm are scheduled for a follow-up visit at 6 weeks ( $\pm 7$  days) after their randomization. At this visit, control subjects will be evaluated and if their ETD symptoms persist (defined as overall ETDQ-7 score  $\geq 3$  or change  $< 0.4$ ), the subjects are eligible for crossover to balloon dilation treatment. Subjects who do not have persistent ETD symptoms are exited from the study after completion of this visit.

Subjects randomized to balloon dilation and crossover subjects are scheduled for the following postprocedure follow-up visits (window):

- 6-Week ( $\pm 7$  days)
- 3-Month ( $\pm 15$  days)
- 6-Month ( $\pm 30$  days)
- 12-Month ( $\pm 45$  days)

The following assessments are required at all follow-up visits:

- Symptom assessment
- Nasal endoscopy examination
- Otoscopy examination

- Tympanogram
- Valsalva evaluation
- Medication use since last study visit
- Ear infections since last study visit
- Revision dilation or additional surgery
- Subject satisfaction
- EQ-5D
- ETDQ-7
- Adverse events

In addition to the assessments noted above, an **audiologic examination is required at the 6-month visit.**

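### Procedure-satisfaction questions share a form with the self-completed primary questionnaire in the dilation arm only, and the protocol does not say which is answered first

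*Combined protocol and SAP*

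**What the plan says.** Section 2.3.1 makes the comparison of mean ETDQ-7 change at 6 weeks between the two arms the primary efficacy endpoint. Section 2.10.1 says of the ETDQ-7: "The questionnaire is designed to be self-completed by the subject". It adds: "The ETDQ-7 CRF may be considered a source document if completed directly by the subject on the CRF". Section 2.10 says that CRFs are on paper.

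Section 2.10.2 (Subject satisfaction) adds a second set of questions for one group: "balloon dilation and crossover subjects will be asked to indicate their satisfaction with the procedure outcome and whether they would recommend the procedure". It then places them: "The subject satisfaction questions will be documented on the ETDQ-7 CRF, which may be considered the source document for the satisfaction ratings".

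Table 1 agrees on who is asked. Satisfaction is ticked at the four postprocedure visits and not at the control arm's 6-week crossover evaluation. The ETDQ-7 is ticked at both.

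Section 2.9.7 gives a bulleted list of visit assessments, introduced by "The following assessments are required at all follow-up visits". Controls continue their current regimen, which may be no medication (Section 2.9.5). No sham procedure or masking is described.

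**The concern.** At the primary time point, a dilation subject may fill in the seven symptom items on a form that also asks for a judgement on the operation and whether to recommend it. A control fills in the same seven items with nothing of that kind alongside. A subject who has just rated the operation, or who reads ahead on a paper form, may answer the symptom items to match.

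Subjects know their arm and the outcome is self-reported, so the comparison already depends on both arms completing the questionnaire under the same conditions. A difference in form content that follows the treatment assignment is one the design does not need. The result is meant to support a 510(k) application (Section 1.2).

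**Working it through.** **1. Is the difference between arms in the text?** Yes. Section 2.10.2 names dilation and crossover subjects, and Table 1 has no satisfaction entry at the control 6-week visit. Crossover subjects are dilated only after their 6-week control assessment, so the primary comparison sets randomized dilation subjects (asked) against controls (not asked).

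**2. Do the documents fix the order of completion?** No.
- Section 2.9.7 lists subject satisfaction, then EQ-5D, then ETDQ-7, but as required assessments.
- Table 1 runs the other way: the ETDQ-7 row is well above, and satisfaction is the last row.
- The similar baseline list in Section 2.9.2 cannot be chronological. It puts the eligibility assessment before the ETDQ-7, yet an ETDQ-7 score of at least 3.0 is itself an inclusion criterion (Section 2.8.1).
- Where the protocol wants an order it states one. The Valsalva maneuver is done "at each follow-up visit after tympanometry is completed", and Section 2.9.4 names three steps that must precede release of an assignment.

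**3. Do the sections agree on who is asked about satisfaction?** Not fully. Section 2.9.7 opens with the control 6-week visit, and its list, which includes satisfaction, applies to all follow-up visits. Section 2.10.2 and Table 1 leave controls out. These two are the more specific texts, but the wording needs to be reconciled.

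**4. Reproducing the plan's sample size.** Inputs from Section 2.6: mean changes −2.15 and −0.85, so a difference of 1.30; SD 1.3; 1-sided alpha 0.025; power 80%; 17 per arm. For a two-sample t-test:
- Standard error = SD × √(2/n) = 1.3 × √(2/17) = 0.446.
- Noncentrality = 1.30 / 0.446 = 2.92, with 2 × 17 − 2 = 32 degrees of freedom and a critical value of 2.037.
- Power = 80.7%. With 16 per arm it is 78.1%.

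So 17 per arm reproduces.

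**5. Sensitivity to an assumed shift.** The documents give no size for any effect of the added questions. Suppose there is no true treatment effect and the dilation-arm mean moves by b points in the device's favour. The chance of a significant result is P(T > 2.037), where T is noncentral t with 32 degrees of freedom and noncentrality b / 0.446.

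| Assumed b | b / 1.30 | Noncentrality | 1-sided type I error |
|---|---|---|---|
| 0 | 0% | 0 | 2.5% |
| 0.1 | 8% | 0.22 | 4.1% |
| 0.2 | 15% | 0.45 | 6.4% |
| 0.3 | 23% | 0.67 | 9.6% |

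With all 40 subjects analysed (20 per arm), the last three rows become 4.2%, 6.9% and 10.6%. A shift in the other direction would cost power instead. If the true difference is 1.30 and the measured one is smaller by 0.1 or 0.2, power at 17 per arm falls from 80.7% to 74.2% or 66.7%.

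**The case against.** A reader might infer from Section 2.9.7 that satisfaction is asked before the ETDQ-7. The documents do not support that, for the reasons in step 2 of the working.

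A reader might also infer that the questionnaire itself is given differently by arm. Section 2.10.1 describes one standardized instrument with one scoring rule. Only the adjacent items differ, and they concern a procedure that controls have not had.

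The remaining objections are these:
- **The form cannot be seen.** The CRF layout is not in the documents. Satisfaction items placed after the seven symptom items would fit Section 2.10.2 equally well and should do little to answers already given. Completion by the subject directly on the CRF is itself conditional in Section 2.10.1. For randomized dilation subjects, 6 weeks is the first postprocedure visit, so no earlier satisfaction question can carry over.
- **The direction is not given.** A pull toward consistent answers would move dissatisfied subjects toward worse scores, so a net benefit to the device cannot be presumed.
- **The trial is open anyway.** Subjects know their arm whatever the layout, so any added effect of two items may be small.
- **The examinations are not arm-specific.** Otoscopy, tympanometry and Valsalva are ticked at both arms' 6-week visits.

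All four stand, and they limit the point to a possible bias. They do not remove it. The placement on a shared form for one arm is stated, nothing requires the ETDQ-7 to come first, and on paper a subject can read ahead or go back and revise. Sites may also differ in the order they use.

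**Conclusion.** The point holds in a limited form. Section 2.10.2 puts dilation-only questions about the procedure on the form that carries the primary outcome, and no section fixes the order of completion. In an open comparison with a subjective endpoint, this leaves an avoidable arm-specific difference in how the primary questionnaire may be completed.

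Whether it biases the result, in which direction and by how much, the documents do not show. The type I error figures of 4.1% to 9.6% rest wholly on assumed shifts of 0.1 to 0.3 points favouring dilation, with the plan's SD of 1.3 and 17 per arm. They show how sensitive a test of this size is to a small shift and do not predict one. The sample size is unaffected.

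The importance is low. The change is worth making because it costs almost nothing.

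**What to change.** - **Section 2.10.2 (Subject satisfaction):** move the satisfaction and recommendation questions to their own CRF page, completed after the ETDQ-7.
- **Sections 2.9.7 and 2.10.1:** state that at every visit where it is given, in both arms, the subject completes the ETDQ-7 first, before the examination and before any satisfaction question, on a page identical in both arms. Completing it before the examination is also sensible for both arms, because Section 2.10.2 notes that a Valsalva maneuver can itself relieve congestion and the ETDQ-7 asks about pressure and feeling clogged.
- **Section 2.9.7:** reconcile its wording on all follow-up visits with Section 2.10.2 and Table 1 on whether controls are asked about satisfaction.

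The cost is one re-laid CRF page and one sentence on order, plus the wording correction. No data, visits, staff or subjects are added.
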